#### 8.1.5 *Artemisia annua* tea and coffee

### Procurement

**Outpatients:** Coffee and tea botanical products will be directly shipped overnight to study patients, who are outpatients by Baesman on behalf of ArtemiLife. Patients without a pod coffee maker will also receive a coffee maker.

The distributor for *Artemisia annua* is as follows:

Baesman Distributors

[name]

[name]

Contact: [[contact]](mailto:[contact])

Subjects randomized to Arm E will have their information entered into the ordering portal of

*IMP: Artemisia annua, Artesunate, Camostat mesilate, Ivermectin,  
Study #: MCC-20-COVID-01-PMC  
Amendment 4 August 28, 2020*

Baesman Distributors website.

**Inpatients:** This botanical product will be dispensed by Artemilife to the IDS pharmacy.

Formulation

Decaf coffee: 450 mg per pod

Tea: 225 mg per bad

Preparation, Storage and Stability

Tea and coffee should be stored at room temperature.

Coffee: Dispense 42, 450 mg pods

Tea: Dispense 84, 225 mg bags

Administration

Refer to the treatment section for specific administration instructions

Patients should be instructed to brew 1 (450mg) coffee pod or 2 (225mg) tea bags in 8 oz of water three times per day Days 1-14.

Drug Interactions

Increased Effect/Toxicity: No known drug interactions

Decreased Effect: CYP2A6 strong inducers may reduce the effects of Artemisia annua

Herb/Nutraceutical Interactions: No known interactions

Pharmacokinetics

Absorption: well absorbed orally

Distribution: Not established

Metabolism: Metabolized by CYP2A6

Half-life elimination: 1hr

Terminal: Not reported

Excretion: Not known

Adverse Events

**Common known potential toxicities, > 10%:**

None reported

**Less common known potential toxicities, 1% - 10%:**

Nausea

Pregnancy: Artemisia annua tea is used for the treatment of malaria in pregnant women and is considered safe

### 8.1.6 Artesunate (Arm F)

#### Procurement

This medication will be dispensed by IDS service.

#### Formulation

100mg tablet

#### Preparation, Storage and Stability

Artesunate should be stored at room temperature.

Dispense 28, 100 mg tablets

#### Administration

Refer to the treatment section for specific administration instructions  
Patients should be instructed to take 2 tablets once a day Days 1-14.

#### Drug Interactions

Increased Effect/Toxicity: No known drug interactions

Decreased Effect: CYP2A6 strong inducers may reduce the effects of Aa and artesunate

Herb/Nutraceutical Interactions: No known drug interactions

#### Pharmacokinetics

Absorption: well absorbed orally

Distribution: Not established

Metabolism: Metabolized by CYP2A6

Half-life elimination: 1hr

Terminal: Not reported

Excretion: Not known

#### Adverse Events

##### **Common known potential toxicities, > 10%:**

Neutropenia

Anemia

Nausea

##### **Less common known potential toxicities, 1% - 10%:**

Diarrhea

Pregnancy: Artesunate is used for the treatment of malaria in pregnant women and is considered safe

## 9. STATISTICAL CONSIDERATIONS

### 9.1 Study Design/Endpoints

This study is a randomized, multi-arm phase II trial. No proven effective therapies currently exist for COVID19 (Sanders J et al. JAMA April 13, 2020), thus a selection design using the frequentist pick-the-winner design will be employed as early screening for promising therapies. The primary objective is to rapidly evaluate multiple potential inhibitors of SARS-CoV-2 viral replication in COVID19 positive patients with high-risk factors in order to decrease clinical deterioration, defined as a less than 2 point decrease in initial COVID 7-POINT ORDINAL OUTCOMES SCALE within 14 days from study entry (primary). As an example, if a person enters the study at ORDINAL SCALE 6 and does not worsen to 4 or less, that is considered a success.

For each arm a phase I lead in portion, six patients per group will be followed in order to evaluate dose limiting toxicities and preliminary safety. If 2 of the first 5 patients or if  $\geq 2$  of 6 patients experience DLT, the regimen will not be considered safe for further evaluation.

The trial will be powered based on the primary endpoint of the rate of patients who will exhibit less than 2 levels of decrease in COVID 7-POINT ORDINAL SCALE from baseline to Day 14. The goal of selection designs is to select with high probability should a superior treatment exist. Note that hypothesis testing or comparisons between arms or with a placebo is not performed with this design and subsequent trials are needed for definitive hypothesis testing of the promising arm.

### 9.2 Secondary Endpoints

#### Secondary endpoints related to efficacy:

- Presence of symptoms or physical examination signs related to COVID-19 disease on Day 14 including: fever, shortness of breath, muscle aches, sore throat, loss of sense of taste or smell, etc.
- Presence of SARS-CoV-2 RNA as detected by polymerase chain reaction (PCR) in nasopharyngeal samples measured minimally on Days 1, 14 and 28
- Proportion of patients with symptoms or physical examination signs related to COVID-19 disease including shortness of breath, muscle aches, sore throat, loss of sense of taste or smell, hospital admission, length of stay, supplemental oxygen requirements, need for mechanical ventilation, intensive care unit admission, etc.

- Time to improvement and resolution of symptoms from baseline to Day 14 and 28
- Oxygen-free days to Day 28
- Ventilator-free days to Day 28
- Vasopressor-free days to Day 28
- ICU-free days to Day 28
- Hospital-free days to Day 28

#### Secondary endpoints related to safety and tolerability up to Day 28

- Incidence, severity, drug-relatedness, and seriousness of adverse events
- Proportion of patients meeting Hy's law criteria
- Proportion of patients with the following Liver function tests (LFT) changes:
  - Any ALT or AST  $\geq 5 \times$  ULN
  - Any AST or ALT  $\geq 3 \times$  ULN together with the appearance of fatigue, nausea, vomiting, right upper quadrant pain or tenderness, fever, rash and/or eosinophilia (eosinophil percent or count above the ULN)
  - Persistent ALT  $\geq 3 \times$  ULN for a period of more than 4 weeks.
- Proportion of patients with significant changes in ECG findings, including heart rate, ECG intervals (PR, QTcB, QTcF), conduction changes, or abnormalities including severe QTc prolongation of  $> 500$  ms.
- Proportion of patients with serious allergic and skin reactions
- Proportion of patients with severe hypoglycemia
- Proportion of patients with retinopathy or macular degeneration
- Proportion of patients with seizure
- Proportion of patients with acute pancreatitis
- Proportion of patients with acute kidney injury
- Proportion of patients with receipt of renal replacement therapy
- Proportion of patients with neutropenia, lymphopenia, anemia, or thrombocytopenia
- All-cause mortality rate

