3.1.4 Ability to provide informed consent by the patient or healthcare proxy

3.1.5 Ability to return for repeated testing and observation to UKHC

3.1.6 Patients must have adequate organ and marrow function measured within the last 30 days as defined below:

- platelets  $\geq 100,000/\text{mcL}$
  - AST(SGOT)/ALT(SGPT)  $\leq 3 \times$  institutional ULN
  - creatinine  $\leq 1.5 \times$  institutional ULN
- OR
- glomerular filtration rate (GFR)  $\geq 45 \text{ mL}/\text{min}/1.73 \text{ m}^2$  unless data exists supporting safe use at lower kidney function values, no lower than  $30 \text{ mL}/\text{min}/1.73 \text{ m}^2$  (see Appendix B).

3.1.7 The effects of therapeutic agents used in this trial on the developing human fetus are unknown. Because therapeutic agents used in this trial may be teratogenic, women of child-bearing potential and men must agree to use adequate contraception (hormonal or barrier method of birth control; abstinence) prior to study entry and for the duration of study participation. Should a woman become pregnant or suspect she is pregnant while she or her partner is participating in this study, she should inform her treating physician immediately. Men treated or enrolled on this protocol must also agree to use adequate contraception prior to the study, for the duration of study participation.

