#### 4.9 Patient Registration to Treatment

To register a patient, the following information should be reviewed by the clinical research nurse (CRN) / clinical research associate (CRA) with the study physician per MCC SOPs to confirm eligibility:

- Copy of COVID19 testing results
- Mobile EKG tracing (outpatients) or standard EKG (inpatients) within 5 days of registration to assess QTc interval
- Eligibility labs, as well as correlative labs to be drawn
- Eligibility Checklist

Once eligibility is confirmed, the CRN/CRA will complete subject registration in the OnCore database (minimum data footprint) for randomization and complete study-required RedCap data forms. To complete the registration process, the CRN/CRA will:

- assign a patient study number
- register the patient on the study in OnCore
- receive the automated treatment arm assignment
- send an email or other communication to the study team of arm assignments.

If a patient is deemed ineligible for treatment their specimens will be retained in the COVID19 BIOBANK if the subject has indicated agreement to specimen collection and long-term storage in the consent form.

At the Day 1 visit or inpatient the following will be completed

- 1) Sign **treatment informed consent** (unless previously e-consented as above)
- 2) Undergo blood testing for eligibility (in subjects who have not had assessment of screening labs within the last 30 days will require blood draw)
- 3) Complete an eligibility questionnaire (age, concurrent diseases, current medications, contact information)
- 4) Undergo a mobile EKG or standard EKG tracing to assess QTc interval (within 5 days of registration)
- 5) Distribute medications, pill diary, and instructions
- 6) Baseline correlative blood sample
- 7) Sputum sample, with OP swab (alternative, if no sputum available)
- 8) Saliva sample
- 9) COVID-19 ordinal scale assessment (See Appendix B)
- 10) Limited visual physical exam unless a more complete exam is clinically indicated.

Day 3 or 4 phone call to assess clinical status and elicit concerns or questions.

Day 7 telehealth (+/- 4 days) is required for all patients to assess toxicity. If a subject has a standard of care telehealth visit during this period, this is also an acceptable toxicity assessment.

Day 10 or 11 phone call to assess clinical status and elicit concerns or questions

Day 14 (+/- 4 days) visit will also be completed in clinic or inpatient hospital.

- 1) Undergo blood testing for toxicity

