- 2) Collection of medications, pill diary and instructions
- 3) Mobile EKG tracing (outpatients) or standard EKG (inpatients) to assess QTc interval
- 4) Correlative blood sample
- 5) Sputum sample, with OP swab (alternative, if no sputum available)
- 6) Saliva sample (optional)
- 7) Nasopharyngeal swab (optional and if indicated for standard of care)\*
- 8) COVID-19 ordinal scale assessment (See Appendix B)
- 9) Toxicity assessment via telehealth or phone call (+/-4 days)

Day 28 (+/- 4 days) visit will also be completed in clinic or inpatient hospital.

- 1) Correlative blood sample
- 2) Sputum sample, with OP swab (alternative, if no sputum available)
- 3) Saliva sample (optional)
- 4) Nasopharyngeal swab (optional and if indicated for standard of care)\*
- 5) Serology testing\*
- 6) COVID-19 ordinal scale assessment (See Appendix B)
- 7) Toxicity assessment via telehealth or phone call (+/-4 days)

Day 40 (+/- 4 days) visit. If serology testing is negative or viral load remains positive, patients will be requested to return for a Day 40 visit (optional) will also be completed via drive through (preferred), clinic or inpatient hospital.

- 1) Correlative blood sample
- 2) Sputum sample, with OP swab (alternative, if no sputum available)
- 3) Saliva sample (optional)
- 4) Nasopharyngeal swab (optional and if indicated for standard of care)\*
- 5) Serology testing (optional and if indicated for standard of care)\*
- 6) COVID-19 ordinal scale assessment (See Appendix B)

\*These are considered standard of care tests

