## 11. STUDY CALENDAR

	Pre-Study	Day 1	Day 3 or 4	Day 7 +/-2 Days	Day 10 or 11	Day 14 +/- 4 Days	Day 28 +/- 4 Days	Day 40*** +/- 4 Days	
Investigational Agent (s) (section 6.0)		A							
Informed consent screening (optional)	X								
Informed consent treatment		X							
Demographics		X							
Eligibility review via medical record	X								
Medical history via medical record review		X				X	X	X	
In-person evaluation		X				X			
Telehealth contact			X a	X a	X a				
Concurrent meds		X-----X							
CBC w/diff, plts*		X				X*			
Serum chemistry, (CMP)*		X				X*			
EKG for QTc		X b				X	X****		
Adverse Events		X-----X							
Standard of Care Nasopharyngeal, Swab and SARS-CoV-2 antibody testing, if clinically indicated (optional)****						X**	X**	X**	
Sputum sample or OP swab (alternative)		X				X	X	X	
Blood sample for Inflammatory cytokines, D-Dimer, CRP, and Procalcitonin and seroconversion (10 mL and 6 mL purple tops)		X				X	X	X	
Blood sample for platelet studies (5 mL yellow top) (optional)		X**				X**	X**	X**	
CPT tube (8 mL speckled top)(optional)		X**				X**	X**	X**	
Saliva sample (optional)		X**				X**	X**	X**	

A - based on assigned arm

\*if not obtained for routine care (for screening phase, if not obtained within the previous 30 days; for treatment phase, if not obtained for routine care of COVID19)

\*\*optional

\*\*\* Day 40 only occurs if patient's serology is negative and viral RNA is positive

\*\*\*\*Only if indicated for routine care

a phone or telehealth contact if the patient is an outpatient

b EKG must be obtained within 5 days of registration

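### The persistent-ALT safety item in section 9.2 cannot be met inside its own Day 28 window, and the retinopathy item is captured only passively

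*Combined protocol and SAP*

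**What the plan says.** Section 9.2 heads the list "Secondary endpoints related to safety and tolerability up to Day 28". Under it stand three liver-test items. The third asks for ALT at or above 3 times ULN lasting "for a period of more than 4 weeks". Further down comes "Proportion of patients with retinopathy or macular degeneration".

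The schedule behind these items is as follows.

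- **Chemistry.** The section 11 calendar marks the metabolic panel at Day 1 and Day 14 (+/-4) and nowhere later. Section 4.9 agrees: "Undergo blood testing for toxicity" appears at the Day 14 visit. Day 28 has research blood, serology and a toxicity check by telehealth or phone. A calendar footnote says that study chemistry is drawn "for treatment phase, if not obtained for routine care of COVID19", so routine-care results may stand in for it.
- **Entry.** Section 3.1.6 says "Patients must have adequate organ and marrow function measured within the last 30 days" and caps AST/ALT at 3 times ULN.
- **Eyes.** No eye examination appears in section 4.9 or the calendar. Section 3.2.7 excludes moderate or severe retinopathy or macular degeneration only where it is already documented.
- **Follow-up.** Section 6.4 ends it at 40 days.
- **Analysis.** One sentence of section 9.5 gives exact confidence intervals for the proportions in 9.2. The safety paragraph of the same section says only that the safety proportions will be summarised. Neither states who is evaluable, and the missing-data rule covers the primary endpoint alone.

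**The concern.** An endpoint that the design cannot register yields zero by construction. If the row is tabulated over all treated patients, a reader cannot tell a liver signal that was looked for and not found from one that could not have been found. Liver signals are relevant here: section 8.1 lists raised liver tests for ivermectin (2%), and liver function abnormalities and jaundice for camostat. Section 2.6 says that safety must be adequately characterised before an agent moves to a large randomised trial.

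The retinopathy item has a milder form of the problem. A proportion is requested, but no method of ascertainment is given and there is no baseline examination to separate new disease from undiagnosed disease.

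**Working it through.** **Inputs.** Window: Day 28 (9.2). Required duration: more than 28 days (9.2). Chemistry: Day 1 and Day 14 +/-4 (11). Entry cap: 3 times ULN (3.1.6). Follow-up: 40 days (6.4). Arm size: 60 (9.3).

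**1. The plan's own exact interval.** The documents give no precision figure for safety items. The nearest is the 90% exact interval for a rate of 0.90 in section 9.3. Clopper-Pearson for 54/60 gives 0.812 to 0.956, width 0.143. The plan prints 0.81 to 0.95 and 0.143, so the method is reproduced (the upper limit is truncated).

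**2. Does the duration fit the window?** 28 − 1 = 27 elapsed days. Counting both end days gives 28, which is still not more than 28. Even with daily routine-care sampling, a rise present on Day 1 could first exceed 28 days on Day 1 + 29 = Day 30, after the window closes.

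**3. Does the scheduled chemistry span it?** 14 − 1 = 13 days, or 18 − 1 = 17 at the latest edge of the visit window. A Day 28 visit held as late as Day 32 would be 31 days after Day 1, but no metabolic panel is taken there.

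**4. Could the rise start before Day 1?** Entry requires ALT no higher than 3 times ULN and the endpoint requires at least 3 times, so the two meet only at exactly 3.0. The eligibility sample may be up to 30 days old, so a rise could begin unseen between that sample and Day 1. It would then precede treatment, and the part inside the window would still be at most 27 days.

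**5. Would one more sample repair it?** A rise first seen on Day 14 needs a value on Day 14 + 29 = Day 43 or later.

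| Added chemistry | Nominal span from Day 14 | Longest span using visit windows |
|---|---|---|
| Day 28 | 28 − 14 = 14 days | 32 − 10 = 22 days |
| Day 40 | 40 − 14 = 26 days | 44 − 10 = 34 days |

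A Day 28 sample never reaches more than 28 days. A Day 40 sample does so only at the extreme of its window, at an optional visit, and past both Day 28 and the 40-day follow-up limit.

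**6. What a printed zero would look like.** The exact upper limit for 0/60 is 1 − 0.05^(1/60) = 0.049 (90% two-sided) or 1 − 0.025^(1/60) = 0.060 (95%). The documents give no true rate. For assumed rates of 1%, 2% and 5%, the chance that an arm of 60 contains at least one true case is 1 − (1 − p)^60 = 45%, 70% and 95%. None of these cases could be counted under the item as written.

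**7. Retinopathy.** Let p be the true rate and s the share that reaches an adverse event form. The chance of no recorded case in 60 is (1 − p·s)^60. With p assumed to be 2%:

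| s | Chance of 0/60 |
|---|---|
| 0% | 100% |
| 25% | 74% |
| 50% | 55% |
| 100% | 30% |

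The count is biased downward by an unknown amount, but it is not fixed at zero.

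**The case against.** The other side has several good points.

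- **Retinopathy.** A reader might infer that it cannot be observed at all. The documents do not support that. Section 6.1 has weekly phone contact and records complications on adverse event forms, and the calendar repeats record review at Days 14, 28 and 40. A clinically diagnosed eye event could be captured, as could seizure or pancreatitis, which also have no scheduled diagnostic test. No agent's adverse event list in section 8.1 names an eye toxicity. What stands is passive ascertainment and probable under-counting.
- **Laboratory data.** A reader might infer that there are none after Day 14. That is true only of scheduled safety chemistry. Routine-care results are anticipated and research blood is drawn at Day 28. Neither rescues the ALT item, by step 2.
- **The reported result.** A reader might infer that the plan will certainly print a false 0% with a tight interval. Section 9.5 leaves open whether safety rows get intervals, states 90% only for the primary rate, and does not say whether unassessed patients count as non-events. The true rate could also be zero.
- **Other liver items.** The items at 5 times ULN and at 3 times ULN with symptoms are observable. Restricting them to the Day 14 sample would discard valid routine-care values.

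None of this removes the conflict between a duration of more than 4 weeks and a window that ends at Day 28.

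**Conclusion.** The persistent-ALT item is wrong as written. It needs more than 28 days inside a window of 27, and the entry cap and chemistry schedule close the remaining routes. Its numerator is zero whatever the true rate, and any 0% reported for it would be uninformative. This rests on taking the Day 28 limit in the 9.2 heading literally and on counting from Day 1. The 4.9% upper limit is an illustration. It applies only if all 60 patients form the denominator and a 90% interval is given, neither of which the plan settles for safety rows.

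For retinopathy or macular degeneration, the supported conclusion is likely under-counting of unknown size, because no ascertainment method is stated.

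The consequence is small. These are descriptive secondary rows with no role in the primary endpoint, the sample size or arm selection.

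**What to change.** - **ALT item.** Delete it from 9.2, or replace it with one that the schedule can measure, for example ALT at or above 3 times ULN at the Day 14 chemistry. Adding a Day 28 chemistry alone would not make the present item measurable. Keeping it would mean extending both the safety window and the chemistry schedule.
- **Denominator.** State in 9.5 that liver-test items are reported over patients with at least one post-baseline chemistry, show that number by arm, and keep counting routine-care values.
- **Eye item.** List it as spontaneously reported or clinically diagnosed events, without an estimated rate, or delete it.
- **Intervals.** Reconcile the two sentences in 9.5 so that it is clear whether safety proportions carry confidence intervals and at what level.

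The cost is a few lines of SAP text and one or two fewer table rows. No visit, sample or patient is added.

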### **9.3 Sample Size/Accrual Rate**

The assumption is that transition rate for deterioration in clinical scale is equal to 20% for the high-risk patients to be enrolled in this trial based on a recent MMWR report from the CDC. The goal is to determine if any of the candidate treatments will exhibit a 50% reduction in deterioration of clinical status (i.e. deterioration rate = 10%). Thus, baseline stability in clinical scale (decrease less than 2 points in COVID 7-POINT ORDINAL SCALE) is assumed to be 80% and an improvement to 90% of all patients remaining stable (decrease less than 2 points in COVID 7-POINT ORDINAL SCALE) is hypothesized. A sample of 60 patients in each arm is proposed. If there is a clear superior treatment as shown in scenarios A and B below, there is at least an 82% selection probability. If the clinical response rate across arms are not very different, the probability of selecting the superior treatment is at 70% and is much higher compared to the other treatments (scenario C); while there is an equal chance of selecting arms that have similar superior efficacy (scenario D).

Scenario A	Response Rate	n	Selection Probability
Trt 1	.80	60	.035
Trt 2	.80	60	.035
Trt 3	.80	60	.035
Trt 4	.90	60	.822

Scenario C	Response Rate	n	Selection Probability
Trt 1	.80	60	.026
Trt 2	.80	60	.026
Trt 3	.85	60	.146
Trt 4	.90	60	.700

Scenario B	Response Rate	n	Selection Probability
Trt 1	.80	60	.002
Trt 2	.80	60	.002
Trt 3	.85	60	.019
Trt 4	.95	60	.949

Scenario D	Response Rate	n	Selection Probability
Trt 1	.80	60	.011
Trt 2	.80	60	.011
Trt 3	.90	60	.421
Trt 4	.90	60	.421

Interim monitoring to assess futility or efficacy will be performed during the trial using the Bayesian posterior probability (See Section 9.6). If a total of 60 patients is enrolled in an arm, the proposed sample size will provide an estimate of clinical success rate with width of a two-sided 90% confidence interval (CI) equal to 0.143 assuming a response rate = 0.90; specifically, a 90% two-sided exact binomial CI = 0.81 – 0.95.

Based on this current design, we plan to enroll a maximum of 240 total patients.

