#### 6.1 Agent Administration

The CURE Alliance Drug Steering Committee will serve as the drug selection committee to identify the appropriate new drugs for each new arm of this clinical trial. Treatment will be administered on an outpatient or inpatient basis provided that entry criteria are met. If emerging data indicates futility of a medication in one or more arms of our study, and was tested in a similar patient population in a randomized clinical trial or trials, the study drug selection committee may recommend removal of that drug treatment arm for futility with approval of the study team. Once a futility endpoint is met in an arm, we will replace that arm with the next appropriate proposed arm with approval of the CURE Alliance Drug Steering Committee. **All subjects receive standard supportive treatment throughout their infection, whether outpatient or during inpatient hospitalization.** Reported adverse events and potential risks are described in Section 10.

Treatment regimens will be evaluated and novel agents selected by the steering committee. Should drug supply become unavailable that arm would pause until drug supply is available.

Regimen Description- Arm C				
Agent	Formulation Strength	Daily Dose	Route	Schedule
Ivermectin	3 mg tablet	12-15 mg	Oral	Weight < 75kg: 4 tabs on Days 1 and 2, (12 mg total daily dose) Weight ≥ 75kg: 5 tabs on Days 1 and 2, (15 mg total daily dose)

Regimen Description- Arm D				
Agent	Formulation Strength	Daily Dose	Route	Schedule
Camostat Mesilate	100 mg tablet	600mg	Oral	2 tab TID after a meal (600 mg total daily dose) Days 1-14

Regimen Description- Arm E				
Agent	Formulation Strength	Daily Dose	Route	Schedule
Artemisia annua tea or coffee	Decaf coffee 450mg per pod Tea 225mg per bag	1350 mg	Oral	One 8oz brewed tea (two bags) or one coffee pod TID Days 1-14

Regimen Description- Arm F				
Agent	Formulation Strength	Daily Dose	Route	Schedule
Artesunate	100mg	200mg	Oral	Two tabs once day (200mg total) Days 1-14

Patients will be assigned to a treatment arm according to the randomization process described in Section 9 of this protocol

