## **9.6 Interim Analysis**

The timing of interim analysis will be based on rate of patient accrual. An initial interim analysis will be performed after 10 patients are randomized in each arm. Futility and efficacy will be assessed in each treatment arm by calculating Bayesian posterior probabilities. The beta distribution for the efficacy/success rate is utilized with a non-informative Jeffrey's prior equal to beta (0.5, 0.5). Specifically, a futility rate  $\leq$  80% will be assumed and the probability for stopping for futility will be set at 70%. An efficacy rate  $\geq$  90% will be assumed and a

probability for early stopping for efficacy set at 90%. Based on these assumptions, the futility stopping boundary for the first 10 patients in each arm is set at  $\leq 7$  patients with clinical stability (i.e. less than 2 point decrease in COVID 7-POINT ORDINAL SCALE) in a specific treatment arm.

The Bayesian methodology allows flexibility in the timing and cohort size in each arm in the conduct of each interim analysis. Thus, depending on patient enrollment and cohort size in each arm, subsequent interim analyses will be performed (e.g. after every 10 additional patients in each arm) and additional stopping bounds will be calculated. ***Real-time assessments of patient response will be critical and will be facilitated by close coordination of clinical and research teams.***

**The decision making process for this trial such as dropping an arm or other changes on how to proceed with the trial will be based on clinical and safety considerations along with newly developing information on COVID19 as well as guidance by results of efficacy estimates and interim posterior probabilities.**

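### The Section 9.3 selection probabilities ignore the planned early stopping: if the Section 9.6 bounds are followed, Scenario A is about .79 with one look and .76 to .78 on fuller schedules, not .82

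*Combined protocol and SAP*

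**What the plan says.** Section 9.3 tabulates four scenarios with n = 60 in every arm. For A (one arm at 90%, three at 80%) and B (95% against 85%, 80% and 80%) it states: "If there is a clear superior treatment as shown in scenarios A and B below, there is at least an 82% selection probability". For C (90% against 85%, 80% and 80%) it says that "the probability of selecting the superior treatment is at 70% and is much higher compared to the other treatments (scenario C").

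Below the table, the same section says: "Interim monitoring to assess futility or efficacy will be performed during the trial using the Bayesian posterior probability". It refers to Section 9.6 but does not say whether the table allows for that monitoring.

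Section 9.6 sets a beta(0.5, 0.5) prior, a 70% posterior threshold for futility (rate 80% or lower) and, for a rate of 90% or higher, a "probability for early stopping for efficacy set at 90"%. The first look is fixed: "the futility stopping boundary for the first 10 patients in each arm is set at" 7 or fewer stable patients. Later looks are left open: "subsequent interim analyses will be performed (e.g. after every 10 additional patients in each arm"). Decisions on arms rest on clinical, safety and external information "as well as guidance by results of efficacy estimates and interim posterior probabilities". Section 6.1 reads more firmly: "Once a futility endpoint is met in an arm, we will replace that arm with the next appropriate proposed arm", subject to approval by the drug steering committee.

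**The concern.** Section 9.1 gives the goal of the design as selecting a superior treatment with high probability, and it rules out hypothesis tests between arms. The Section 9.3 probabilities are therefore the main evidence that 60 per arm is enough; the confidence-interval width is a separate precision argument. A reader will take 82% as the performance of the trial as planned.

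Early stopping can only be ignored if it rarely affects the best arm. Here it does affect it. A look at 10 patients can drop a truly good arm, and an efficacy stop freezes an arm's observed rate at a small n, where an ordinary arm can look excellent by chance. Both lower the chance that the best arm is picked.

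**Working it through.** **Inputs.** From Section 9.3: n = 60 per arm, four arms, and the scenario rates. From Section 9.6: the Jeffreys beta(0.5, 0.5) prior; futility if P(rate ≤ 0.80 | data) ≥ 0.70; efficacy if P(rate ≥ 0.90 | data) ≥ 0.90; first look at 10 per arm, with every 10 as the example for later looks. Assumed here, because the plan has no final selection rule: the winner is the arm with the highest observed rate among arms not stopped for futility. Replacement arms are not modelled.

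**Step 1: reproduce the table.** With no looks and ties counted as no selection, P(select arm 4) = Σₓ P(X₄ = x) · Πⱼ P(Xⱼ < x), where X ~ Binomial(60, p).

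| Scenario | Computed | Printed |
|---|---|---|
| A | .8219 | .822 |
| B | .9488 | .949 |
| C | .6957 | .700 |
| D | .4206 | .421 |

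The inferior arms match too (A: .0350 against .035). The tie convention also shows in the printed sums: A, 3 × .035 + .822 = .927; D, 2 × .011 + 2 × .421 = .864. The remainder is the probability of a tie for first place. The table is thus the fixed-n calculation without stopping.

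**Step 2: derive the bounds.** After x stable patients of n, the posterior is beta(x + 0.5, n − x + 0.5). At n = 10, P(rate ≤ 0.80) is .795 at 7/10 and .533 at 8/10, which confirms the stated bound of 7 or fewer. Even 10/10 gives P(rate ≥ 0.90) = .858, so no efficacy stop is possible at that look.

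| n | 10 | 20 | 30 | 40 | 50 |
|---|---|---|---|---|---|
| Futility if ≤ | 7 | 15 | 22 | 30 | 38 |
| Efficacy if ≥ | none | 20 | 29 | 39 | 48 |

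**Step 3: chance of stopping an arm.** P(X ≤ 7) for Binomial(10, 0.90) is .070, and for Binomial(10, 0.80) it is .322. So the fixed look drops a true 90% arm 7.0% of the time and an 80% arm 32% of the time. By n = 50 the 90% arm has been dropped with probability 7.5% (looks at 10/30/50) or 9.2% (every 10). With both rules every 10, it stops early for efficacy 24% of the time.

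**Step 4: selection probability with stopping.** Each arm's path was enumerated exactly through the looks, and the four arms were then compared on observed rate. Cells show ties as no selection / ties split at random.

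| Schedule | A | B | C |
|---|---|---|---|
| No looks | .822 / .855 | .949 / .962 | .696 / .743 |
| Futility at 10 only | .792 / .818 | .941 / .954 | .680 / .721 |
| Futility every 10 | .7845 / .809 | .941 / .953 | .677 / .716 |
| Both rules at 10/30/50 | .781 / .806 | .905 / .924 | .668 / .706 |
| Both rules every 10 | .764 / .786 | .879 / .900 | .654 / .689 |

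Monte Carlo runs agree within .0015. Treating an efficacy stop as ending the trial, rather than comparing by rate, changes A by no more than about .001. D stays at about .42 per superior arm when ties are not counted.

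**Step 5: size of the loss in A.** Ties as no selection: .822 − .792 = .030, up to .822 − .764 = .058. Ties split: .855 − .818 = .037, up to .855 − .786 = .069.

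**Sensitivity to schedule (A, both rules, ties as no selection).** Looks at 10 and 35, or at 10 and 40, leave .79. Looks at 10/25/40/55 give .784. Looks every 5 patients from 10 onward give about .72.

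**The case against.** The best defence is that the printed A, B and D values are correct for what they show. The n column reads 60 in every arm, and the monitoring is announced in the same section, so a careful reader could infer that the table is for full enrolment. That is partly fair, but an inference is not a statement. The only conditional wording, about a total of 60 being enrolled in an arm, is attached to the confidence interval and not to the table.

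Second, with ties split, the one fixed look leaves A at .818, practically 82%. That is true, but the matching starting value is then .855, so the loss remains; and the plan states no tie rule.

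Third, the posterior probabilities are guidance, later looks are only an example, and the approval clause in Section 6.1 softens the contrast with Section 9.6, since it may cover only the choice of replacement. This stands as a limit: the losses apply only as far as the bounds are followed, and .76 to .78 is illustrative of plausible schedules. Sections 6.1 and 9.6 need clarifying rather than being in plain contradiction.

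Fourth, dropping 80% arms quickly is a purpose of the rule, and the loss is modest for a screening trial. Both are true. They argue against changing the sample size, not against stating the performance correctly. The difference between .696 and .700 in C is minor, and nothing here depends on it.

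**Conclusion.** The point holds. The Section 9.3 table describes a design with no early stopping and does not say so. If the Section 9.6 bounds are followed, the claim of at least 82% fails in Scenario A on the table's own counting: .79 with the single look that the plan fixes, and .76 to .78 on plausible fuller schedules with both rules. The 70% quoted for C falls to between .680 and .654 on the same counting. Scenario B stays above 82% on every schedule tabulated.

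The conclusion rests on the assumed selection rule (highest observed rate among arms not stopped for futility), on the bounds being applied, and on leaving out replacement arms and safety stopping in the run-in. The direction of the loss in A does not depend on how ties are handled. It is a modest shortfall that should be corrected in the text; it does not undermine the choice of 60 per arm.

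**What to change.** Either of two changes is enough.

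- **Minimum.** Add one sentence under the table: *These probabilities assume 60 patients in every arm and no early stopping; ties are counted as no selection.* Correct C to .696.
- **Preferred.** Fix the look schedule, the final selection rule and the tie rule; recompute the table by simulation under the Section 9.6 bounds; and replace the 82% and 70% statements with the results. If looks are every 10 patients, the bounds in Step 2 can be printed in Section 9.6.

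In both cases, state whether the bounds are binding or advisory so that Sections 6.1 and 9.6 read the same way, and say whether the maximum of 240 patients includes replacement arms.

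The cost is one sentence, or a short simulation and a revised table. The drawbacks are slightly less favourable figures and, under the preferred option, a look schedule committed to in advance. The sample size stays as it is.
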